8.0 Statistical Considerations

8.1 Hypothesis to be Tested

This is a preliminary, prospective, single-arm study to assess the safety of AMDC-USR in males with SUI. The study is not powered statistically for any measurable outcomes.

8.2 Sample Size

The study will treat up to 30 patients at up to 5 clinical sites. Because this is a preliminary study, no formal statistical determination of sample size was performed.

8.3 General Analysis

Statistical analyses will be performed using SAS[®] for Windows[®] (release 9.3 or higher) or other widely accepted statistical software. Continuous variables will be reported as means and standard deviations unless otherwise noted. Categorical variables will be reported as percents. Ninety-five percent (95%) confidence intervals for all endpoint variables will be presented. Survival analysis techniques such as Kaplan-Meier or Cox Proportional Hazards may be incorporated if censoring of data occurs.

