6.2 Inclusion and Exclusion Criteria

Patient eligibility for enrollment shall be based on known information at the time of the screening. Information obtained at a later date may contradict these criteria, but this will not be considered a deviation to the CIP.

Inclusion Criteria

A patient is deemed suitable for inclusion in the study if the patient meets the following criteria:

1. Male, at least 18 years old, with primary symptoms of SUI following prostate surgery that occurred at least 12 months prior to enrollment, as confirmed by medical history and clinical symptoms, including a focused incontinence evaluation.
2. Patient has undergone prostate surgery, such as radical prostatectomy or prostate resection, but has not undergone radiation therapy, cryotherapy, or high-intensity focused ultrasound of the prostate.
3. SUI severity must be ≥ 10 g and < 400 g of urine leakage over 24 hours, as determined by a 24-hour pad test during screening.²

² Moore, et al.⁵ suggest > 4 g as a minimum pad weight gain for incontinence in men, but that the upper limit for normal pad weight gain should be 8 g. Thus, > 8 g would be considered incontinence in men. Kumar, et al.⁶ suggest > 400 g/24 h is high-grade incontinence (or total incontinence), and recommend men in this category receive an artificial urinary sphincter.

4. Patient has failed to achieve acceptable resolution of SUI symptoms following prior therapy.

Exclusion Criteria

A patient is excluded from enrollment into the study if any of the following are true:

Patient History-based Criteria:

1. Simultaneously participating in another investigational drug or device study or has completed the follow-up phase for the primary endpoint of any previous study less than 30 days prior to the first evaluation in this study.
2. Previously treated with an investigational device, drug, or procedure for urinary incontinence within 6 months prior to signing consent.
3. Has ever been treated with a cell therapy for urinary tract dysfunction.
4. Has an artificial sphincter.
5. Previously treated with a periurethral balloon or adjustable sling for urinary incontinence.
6. Symptoms of stress urinary incontinence prior to prostate surgery.
7. Symptoms of only urge urinary incontinence as noted by basic evaluation of etiology from patient medical history, including a focused incontinence history.

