6.4 Variables to be Measured to Demonstrate Achievement of Endpoints

Safety endpoints will be measured as follows:

- Study product-related SAEs reported through 24-month follow-up;
- Study product-related, biopsy procedure-related, and injection procedure-related adverse events reported through 24-month follow-up; and
- Ultrasound/bladder scan determination of PVR volume on the day of injection and at 1, 3, 6 and 12 months post-treatment.

The secondary efficacy endpoints will be measured as follows:

- Reduction in amount of urine leakage from baseline as assessed by 24-hour pad test at 1, 3, 6 and 12 months;
- Change from baseline in patient-reported outcomes for incontinence symptom severity and QOL will be measured by ICIQ, IQOL score and subscores, I-PSS, and PGI-S score at 1, 3, 6 and 12 months; and
- Change in patient-reported incontinence symptom severity will also be measured by PGI-I score at 1, 3, 6 and 12 months.

In addition, change from baseline in patient symptoms of ED will be measured by the IIEF-5 questionnaire at 1, 3, 6 and 12 months. Patient clinical information including details of prior procedures for prostate surgery, underlying reason for prostate surgery, underlying disease severity, and any procedures or revisions following the incident procedure to address disease or SUI symptoms will be collected and evaluated as appropriate.

The clinical data will be collected on standardized Case Report Forms (CRFs). The schedule for assessments is summarized in Table 6.1.

Table 6.1. Data collection schedule

	Screening	Biopsy	Post-biopsy	Treatment	Post-treatment						
	Visit 1	Visit 2	Phone	Visit 3	Phone	Phone	Visit 4	Visit 5	Visit 6	Visit 7	Phone
	Week 1-8 ^a	Week 2-10	Week 3-11	Day 0	Day 1-2	Week 1	Month 1	Month 3	Month 6	Month 12	Month 24
Event	Screening	Biopsy	Follow-up	Injection	Follow-up	Follow-up	Office Visit	Office Visit	Office Visit	Office Visit	Follow-up
Informed Consent	X										
Inclusion/Exclusion ^b	X										
Medical History	X										
Clinical Assessment	X						X	X	X	X	
Physical Examination	X										
Vital Signs	X										
Medication Log	X	X	X	X	X	X	X	X	X	X	X
Urinalysis	X			X			X	X	X	X	
Urine Culture ^c				X							
Bladder Stress Test	X									X	
24-hour Pad Test	X			X			X	X	X	X	
Post-void Residual Volume	X			X			X	X	X	X	
Questionnaires ^d : ICIQ, IQOL, PGI-S, I-PSS, IIEF-5	X			X			X	X	X	X	
Questionnaire ^d : PGI-I							X	X	X	X	
Blood Samples	X ^f						X			X	
Cystoscopy	X ^e			X						X	
Muscle Biopsy		X									

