6.5 Measures to be Taken to Avoid or Minimize Bias

This preliminary, prospective, single-arm study is intended to collect information regarding the safety and potential efficacy of intrasphincteric injection of AMDC-USR for the treatment of male SUI that develops following prostate surgery. Study patients will be enrolled at up to 5 sites and uniform definitions will be used for study endpoints.

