7.3 Pre-enrollment (Visit 1) – Screening

Screening tests may be completed in up to 3 screening visits to accommodate site-specific scheduling. It is recommended that screening tests conducted in Visit 1 be completed within 8 weeks preceding the biopsy visit. Bloodborne pathogen testing must be completed within 30 days before the biopsy procedure. If more than one visit is required, adverse events that occur after the patient signs the consent form shall be recorded during subsequent visits.

After providing informed consent, the patient will have a medical history (including a urinary incontinence-focused history), a physical examination (including assessment of vital signs), a clinical assessment, and a medication assessment. Urine samples will be collected to test for nitrites and leukocyte esterase. If the urine test is positive for leukocyte esterase or nitrites, then a

urine culture may be performed. The patient will undergo a bladder stress test (please refer to Appendix A for the Instructions for the Bladder Stress Test) and will complete a 24-hour pad test. Patients will be instructed on how to perform the 24-hour pad test (please refer to Appendix B for the Instructions for the 24-Hour Pad Test) and will be provided with sufficient preweighed pads to complete the test. The completed 24-hour pad test must be returned before or at the next scheduled screening visit. A PVR urine volume will be measured with ultrasound/bladder scan. Patients will complete the following questionnaires: ICIQ, IQOL, PGI-S, I-PSS, and IIEF-5. Blood samples will be collected to assess for PSA levels, bloodborne pathogens, hematocrit, hemoglobin, WBC count, blood urea nitrogen (BUN) or urea, and creatinine. Patients will undergo cystoscopy for evaluation of the appearance of urethral and bladder tissue. An existing cystoscopy evaluation can be used if performed within 6 months prior to the time of consent. It is recommended that screening tests be performed from the least invasive test to the most invasive. Adverse events reported by the patient after informed consent is obtained will be recorded.

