7.6.1 Post-Biopsy Follow-up (Phone)

Within 5 business days after the biopsy procedure, patients will be contacted by phone to determine whether any adverse events have occurred and whether any updates to the medication log are necessary.

7.7 Procedure (Visit 3) – Treatment Day 0

Approximately 12-13 weeks after the muscle biopsy, patients will return to the clinic for a brief outpatient procedure. At the start of the visit or before the visit, patients will provide a completed 24-hour pad test and complete the ICIQ, IQOL, PGI-S, I-PSS, IIEF-5 questionnaires. The 24-hour pad test and questionnaire data collected on the day of injection will be used as the baseline data. Prophylactic antibiotics will be given prior to the injection procedure. Prior to injection, patients will have a urine sample collected to test for nitrites and leukocyte esterase. If the urine test is positive for leukocyte esterase or nitrites, a urine culture must be performed and the injection will be delayed. A negative urine dipstick for leukocyte esterase and nitrites is required in order to undergo AMDC-USR injection. Ultrasound may be performed to aid in the injection procedure. Under direct vision, multiple injections will be performed to circumferentially distribute AMDC-USR within the striated muscle of the urethral sphincter. After the injection is completed, the injected area will be examined for any excessive bleeding or excessive trauma. Prior to discharge, patients will demonstrate a normal void and will have their PVR urine volume determined by ultrasound/bladder scan. The medication log will be updated if necessary. Any adverse events occurring since the last visit or before, during, or after the injection procedure will be recorded and reported as appropriate.

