8.4 Missing Data

Missing data may be addressed using complete case analysis or multiple imputation.

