APPENDIX B
24-Hour Pad Test

All patients will have a 24-hour pad test as part of the screening procedures and at 1-month, 3-month, 6-month and 12-month follow-ups. The 24-hour pad test should be completed the day before each scheduled visit.

24-hour pad test

[Redacted]

[Redacted]

[Redacted]

[Redacted]

[Redacted]

[Redacted]

[Redacted]

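### Does Appendix B's omission of the Day 0 pad test, with no stated scale for the reduction, leave the pad-test endpoint undefined?

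*Combined protocol and SAP*

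**What the plan says.** Sections 6.3.2 and 6.4 make pad-test leakage a secondary endpoint: "Reduction in amount of urine leakage from baseline as assessed by 24-hour pad test at 1, 3, 6 and 12 months". Section 7.7 (Visit 3, Day 0) has the man hand in a completed pad test at or before the start of the visit, and then says: "The 24-hour pad test and questionnaire data collected on the day of injection will be used as the baseline data". The pad-test row of Table 6.1 is marked at screening, Visit 3 and months 1, 3, 6 and 12.

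Appendix B gives a shorter list: "All patients will have a 24-hour pad test as part of the screening procedures and at 1-month, 3-month, 6-month and 12-month follow-ups". Its next sentence places the test on the day before each scheduled visit. The rest of the appendix is redacted.

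For analysis, section 8.3 says "Continuous variables will be reported as means and standard deviations unless otherwise noted", with percents for categorical variables and 95% confidence intervals for all endpoint variables. Section 8.4 says "Missing data may be addressed using complete case analysis or multiple imputation". Sections 8.1, 8.2 and 8.5 say that the study is unpowered, that its size was not calculated, and that it cannot support definitive efficacy statements.

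**The concern.** Each man is his own control (section 8.5), so every pad-test result depends on the pre-treatment value. Section 7.3 sends sites to Appendix B for the pad-test instructions, and a site that took its visit list from there could miss Day 0. The only other pre-treatment value is the screening test, which makes a poor baseline for two reasons. It decided entry ("SUI severity must be ≥ 10 g and < 400 g of urine leakage over 24 hours"), so it is a selected measurement. It can also be old: "It is recommended that screening tests conducted in Visit 1 be completed within 8 weeks preceding the biopsy visit", and injection follows biopsy by about 12 to 13 weeks.

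The scale matters as well. A mean change in grams and a mean percent change can point in opposite directions in the same men, and neither section 6.4 nor section 8.3 names one. Section 6.5 says that "uniform definitions will be used for study endpoints", so an endpoint with an uncertain baseline and an unstated scale seems to fall short of the plan's own commitment. If either choice were made after the data were seen, the reported result could change.

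**Working it through.** **1. The schedules side by side.**

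| Source | Screening | Day 0 | Months 1, 3, 6, 12 | Total |
|---|---|---|---|---|
| Table 6.1 | yes | yes | yes | 6 |
| Visit sections 7.3, 7.7, 7.8.3 to 7.8.6 | yes | yes, named as baseline | yes | 6 |
| Appendix B, list | yes | not named | yes | 5 |
| Appendix B, next sentence | n/a | covered if Visit 3 counts as a scheduled visit | n/a | n/a |

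Two of the three lists agree, and the only one that names a baseline is unambiguous. The Appendix B list is incomplete but does not name a different baseline.

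**2. What a screening baseline would do.** From the documents: entry range 10 to <400 g; the gap from screening to injection can be 8 + 12 = 20 to 8 + 13 = 21 weeks. The documents give no leakage distribution, so the rest is assumed: lognormal true levels, independent day-to-day variation, no true change, and men kept only if the screening value is in range. Shift = mean follow-up / mean baseline − 1. Without a true change, mean follow-up equals mean Day 0.

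With proportional day-to-day variation:

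| Median, between-man log-SD, within-man log-SD | Mean screening | Mean Day 0 | Shift from screening | True 30% fall reads as |
|---|---|---|---|---|
| 60 g, 1.0, 0.4 | 88.0 g | 93.0 g | +5.6% | 1 − 0.7 × 1.056 = 26% |
| 100 g, 1.0, 0.4 | 117.6 g | 129.0 g | +9.7% | 1 − 0.7 × 1.097 = 23% |
| 150 g, 1.2, 0.5 | 135.0 g | 166.8 g | +23.5% | 1 − 0.7 × 1.235 = 14% |

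(Shifts use unrounded means.) With less variation the shift shrinks: 60 g with log-SDs 1.0 and 0.3 gives about +3%. With a constant scatter of 15, 30 or 45 g the sign reverses: −1.4%, −4.3% and −7.5% at median 60 g; −0.1%, −0.6% and −1.3% at median 150 g. From Day 0 the shift is zero in every case.

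If only 6 of 30 men (one of five equal sites) had screening in place of Day 0, the mixed baseline in the first row is 0.8 × 93.0 + 0.2 × 88.0 = 92.0 g, a shift of 93.0/92.0 − 1 = 1.1%. In the third row it is 0.8 × 166.8 + 0.2 × 135.0 = 160.4 g, a shift of 4.0%.

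**3. What section 8.4 would do with those 6 men.** Neither method it names puts the screening value in place of Day 0. Complete-case analysis would drop them, leaving 24. If the missing tests are unrelated to leakage, the mean is not biased and the interval widens by about √(30/24) = 1.12.

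**4. Scale.** With within-man log-SD w and no true change, mean percent change from Day 0 averages exp(w²) − 1: exp(0.16) − 1 = 17% for w = 0.4 and exp(0.25) − 1 = 28% for w = 0.5. A true 30% fall would read as 1 − 0.7 × 1.174 = 18% or 1 − 0.7 × 1.284 = 10%. An invented example within the entry range shows a conflict of sign: baselines of 20, 50 and 350 g and follow-ups of 5, 20 and 400 g give reductions of 15, 30 and −50 g, mean −1.7 g, but 75%, 60% and −14%, mean 40%. Mean percent change is therefore a poor summary, but the plan does not name it. The endpoint is an amount, the entry criterion measures it in grams, and the default summary is a mean. Mean gram change from Day 0 is unbiased for the mean change in these men, and shows a true 30% fall as 30%.

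**The case for a change.** The strongest case for acting is that the omission is real and cheap to correct. It stands in a complete, readable sentence, so redaction does not explain it. The test it omits is the one that cannot be repeated once the man is treated. Section 8.4 does not choose between its two methods and does not address a missing baseline, and no sentence in the plan says grams. One added visit in Appendix B and a sentence each in 8.3 and 8.4 would settle everything.

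The first part stands: the Appendix B list does not match section 7.7 or Table 6.1, and an editor should align them at the next routine revision. The rest carries less weight. Appendix B is cited for how to do the test; the visit section and the data-collection schedule say when, and both include Day 0. A site would have to overlook both of them, and Appendix B's own next sentence, to miss it. The phrase on uniform definitions in section 6.5 sits in a sentence about enrolling at up to 5 sites, and reads more naturally as consistency between sites than as a commitment on analysis scale. Adding medians, counts of dry men or a log ratio would be a matter of preference; no consistent gain in precision was shown for the median percent change.

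**Conclusion.** The concern does not call for a change. The baseline is defined in section 7.7 and the test is scheduled in Table 6.1. Followed as written, the plan collects Day 0 and reports a mean change in grams with its SD and 95% confidence interval, which is valid for a descriptive secondary endpoint. The mismatch is five listed tests against six: a clerical slip. The unstated scale and the lack of a specific rule for a missing Day 0 test are details that an analyst would fill in the obvious way.

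The shifts of −7.5% to +23.5% arise only if screening replaced Day 0 for every man, which no section proposes. They rest on assumed distributions, and their sign depends on the assumed form of day-to-day variation. At one site in five, the proportional-variation rows tabulated give about 1% to 4%. This conclusion assumes that sites work from section 7.7 and Table 6.1, and that amount is read as grams. If the report instead used mean percent change or a screening baseline as its main result, that would be a fault in the report, and the wording of 6.4 and 7.7 would be grounds to challenge it.

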8.4 Missing Data

Missing data may be addressed using complete case analysis or multiple imputation.

8.5 Limitations of the Study

This preliminary study with a small sample size may limit the ability to generalize results to a larger population. The sample size is insufficient to allow definitive statements regarding efficacy. Patients will serve as their own controls with quantitative and qualitative measures of incontinence assessed before treatment and compared to the same measures at various times after treatment.

9.0 Deviations from Clinical Investigation Plan

Investigators are not allowed to deviate from this CIP without prior authorization by the sponsor except under emergency situations when necessary to preserve the rights, safety, or well-being of study patients.

Deviations and noncompliances will be recorded together with an explanation. Deviations or noncompliances that impact the rights, welfare, or safety of patients shall be reported to the sponsor and the IRB/REB as required and as soon as possible.

If appropriate, corrective and preventive actions will be discussed by the sponsor, investigator, or the IRB/REB to determine a suitable course of action.

10.0 Data Collection and Reporting

10.1 Electronic Case Report Forms

Patient data will be collected and entered by trained personnel at the clinical site into electronic Case Report Forms (eCRFs) through an electronic data capturing (EDC) system. This is a secure, web-based system, allowing those with permission to access data from any location at any time. Source data is to be retained for data entered into the EDC system. Data obtained and simultaneously entered into the EDC system may also serve as source documentation. Site personnel are required to undergo data entry training and will have unique login names and passwords in order to enter patient data. In accordance with 21 CFR Part 11, the EDC system creates a secure, computer-generated, time stamped audit trail to record the date and time of operator entries and actions that create, modify, or delete electronic records.

10.2 Data Reporting

Progress reports and a final report at the conclusion of the clinical study will be submitted by the investigators and sponsor to the regulatory authorities and IRB/REB as required by local regulations.

11.0 Data Management

11.1 Data Entry and Data Review

Each principal investigator or appropriately trained designee shall enter the clinical data into the EDC system on standardized CRFs. Investigators will provide all applicable clinical data and documentation to the sponsor. Patient data and documents pertaining to the study will be kept and archived by the sponsor. Data will be reviewed for missing data, data consistency, and reasonableness of responses. Discrepancies will be resolved through a formal query process involving direct contact with investigators or research coordinators. The data coordinating center is responsible for database management, data verification, data archiving, and data retention.

As needed to assist the sponsor in its research (e.g., during evaluation of an adverse event), data will be accessible to the sponsor, the participating investigators, the manufacturer, and companies or individuals the sponsor authorizes.

Cook Research Incorporated the data coordinating center, is physically located in the United States. Therefore, information collected within a country outside of the United States will be transmitted to the United States. Personal information will be protected by fair trade practices and in accordance with all applicable laws.

11.2 Data Monitoring Arrangements

The conduct of the clinical study will be supervised through a process of centralized and on-site monitoring. The data coordinating center will remotely monitor the study for data completeness and for adverse events. On-site monitoring will be implemented as necessary throughout the course of the study. The investigator/institution will provide direct access to source data/documents for study-related monitoring, audits, IRB/REB review, and regulatory inspection. Written procedures for monitoring the study are maintained by the data coordinating center and are summarized in Appendix C.

12.0 Procedures for Reporting Adverse Events

Adverse events are to be reported to the data coordinating center using the appropriate CRF. In cases of adverse drug reactions or SAEs, completed forms will be submitted to the data

coordinating center as soon as possible upon knowledge of the event. The data coordinating center will review the information submitted for possible reporting to the sponsor. Adverse events will be assessed in terms of relationship to product, relationship to biopsy procedure, relationship to injection procedure, severity, subsequent treatment/intervention required, and resolution status. Follow-up of all adverse events will be conducted per institutional standard of care.

The sponsor shall, if required according to applicable regulations, report the event to the appropriate regulatory authority. (Expedited reporting is required for serious and unexpected suspected adverse reactions [SUSARs].) If indicated, all principal investigators and clinical sites will be notified of applicable events by the sponsor. The principal investigator or designee will notify his/her IRB/REB of applicable events according to institutional guidelines.

